**Table 16: Probabilities of Observing Varying Frequency of Response Under Different True Response Rates (40 Subjects)**

No. Response (r)	Probability	Event Rate			
		20%	30%	40%	50%
8	Prob(no. resp <= r   true p)	0.593	0.111	0.006	0.000
9	Prob(no. resp <= r   true p)	0.732	0.196	0.016	0.000
10	Prob(no. resp <= r   true p)	0.839	0.309	0.035	0.001
11	Prob(no. resp <= r   true p)	0.912	0.441	0.071	0.003
12	Prob(no. resp <= r   true p)	0.957	0.577	0.129	0.008
13	Prob(no. resp <= r   true p)	0.981	0.703	0.211	0.019
14	Prob(no. resp <= r   true p)	0.992	0.807	0.317	0.040
15	Prob(no. resp <= r   true p)	0.997	0.885	0.440	0.077
16	Prob(no. resp <= r   true p)	0.999	0.937	0.568	0.134

Prob=probability; No.=number.

## 9.5 Toxicity Stopping Rule

Any dosing adjustment made during assessment of DLTs in the DLT cohort will be applied as the dosing schedule for remainder of the study. During the study, a stopping rule for observation of excess toxicity will be implemented. The rate of AEs that would meet the DLT criteria (Section 8.5.6) of the study will be used to establish stopping guidelines for excess toxicity. For the duration of therapy, any event that occurs and is at least possibly related to study treatment, and that meets the criteria set out for DLT, will be counted. Sequential boundaries will be used to monitor the DLT rate (Ivanova et al 2005). Accrual will be halted if excessive numbers of subjects with DLTs are observed, that is, if the number of subjects with DLTs is equal to or exceeds  $b_n$  out of  $n$  subjects who start Cycle 1. This is a Pocock-type stopping boundary that yields the probability of crossing the boundary at most 20% for DLTs when the presumed rate of DLTs is equal to approximately 20% (Table 17). In addition to this stopping rule, Astex may stop enrollment and/or terminate the study for safety concerns.

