#### 4.1.1 Dose-Limiting Toxicity Cohort

[figure not shown]
The first 6 to approximately 18 subjects enrolled, the DLT cohort, will be evaluated to confirm that the dosing of oral decitabine/cedazuridine in combination with magrolimab is well tolerated (Section 8.5.6). Due to the low incidence of magrolimab DLTs (please reference Investigational New Drug [IND] 147229 for the magrolimab Investigator Brochure), it is expected that most DLTs will be related to oral decitabine/cedazuridine, especially those related to neutropenia, thrombocytopenia, GI toxicity, and infection. Thus, a DLT should generally be considered related to oral decitabine/cedazuridine unless the investigator feels that a DLT is related to magrolimab. The DLT period will last the first 2 cycles of oral decitabine/cedazuridine treatment as defined in Section 4.1. Evaluation of the cohort will end when a tolerated dosing is identified, or the study is stopped due to toxicity. Oral decitabine/cedazuridine and magrolimab dosing will initiate as outlined in Section 4.5. If there are DLTs associated with magrolimab that occur in the DLT cohort, the investigator in consultation with the Astex medical monitor and the Data and Safety

Review Committee (DSRC) will determine if a dose modification of magrolimab is appropriate (see Section [6.6.2](#) for magrolimab dose modification recommendations).

The dosing reduction process for oral decitabine/cedazuridine-associated DLTs will follow a 3+3 design ([Figure 2](#)), as follows:

- The first 6 subjects will be evaluated for myelosuppression and other DLTs (Section [8.5.6](#)).
- If fewer than 2 subjects among the first 6 (<33%) experience a DLT (Section [8.5.6](#)), the current dosing level will be maintained, and no further DLT cohort evaluation will be conducted.
- If a DLT occurs in 2 or more of the initial 6 subjects, then oral decitabine/cedazuridine dosing will be reduced 1 level ([Table 9](#)) and 3 more subjects will be enrolled at that dosing level.

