#### **8.5.6 Definition of Dose-limiting Toxicities**

Dose-limiting toxicities are defined as any of the following toxicities at least possibly related to the treatment regimen as determined by the DSRC:

- Drug-related Grade  $\geq 3$  non-hematologic events (except nausea, vomiting, or diarrhea if the events do not require tube feeding, total parenteral nutrition, or require or prolong hospitalization).
- Grade 4 neutropenia and thrombocytopenia, not present prior to dosing, that last 28 days or longer should be considered a DLT unless clearly and solely due to the underlying disease.

- If the investigator suspects that the development of Grade 4 neutropenia or thrombocytopenia is drug related and the event continues for 7 days in Cycle 1, a BM assessment (no later than the 14th day of Grade 4 cytopenia) may be done, at the discretion of the investigator, to assist with the determination of DLT.
- Delay of >2 weeks after Cycle 1 is complete due to drug-related toxicity. That is, if initiation of Cycle 2 is delayed for drug-related toxicity, the DLT window will expand accordingly.
- Establishment of an MTD is not a goal of this study. However, the DSRC will assess the occurrence of DLTs in the DLT cohort (Section 4.1.1) to help ensure the study drug combination is safe. The DLT period has been defined as the first 2 cycles of oral decitabine/cedazuridine (from the start of administration to Cycle 1 Day 28) in the first 6 to approximately 18 subjects.

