**Table 17: Criteria for Excess Toxicity for an Acceptable Dose-limiting Toxicity Rate of 20%**

Number of Subjects, n	1	2	3-4	5-7	8-10	11-14	15-17	18-21	22-25	26-28
Boundary, b	-	2	3	4	5	6	7	8	9	10
Number of Subjects, n	29-32	33-36	37-40	41-44	45-48	49-52	53-56	57-60	61-64	65-69
Boundary, b	11	12	13	14	15	16	17	18	19	20
Number of Subjects, n	70-73	74-77	78-81	82-85	86-90	91-94	95-98	99-100		
Boundary, b	21	22	23	24	25	26	27	28		

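### The Section 9.5 toxicity boundary is read at all subjects who have started Cycle 1, so subjects with incomplete follow-up raise it and can mask a crossing among earlier subjects

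*Combined protocol and SAP*

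**What the plan says.** Section 9.5 stops accrual for excess toxicity once the count of affected subjects is at or above a boundary b_n. The index n counts "subjects who start Cycle 1. This is a Pocock-type stopping boundary that yields the probability of crossing the boundary at most 20% for DLTs"; that limit refers to a true DLT rate of about 20%. Table 17 gives the boundary for n from 1 to 100. It rises by roughly one DLT for every four subjects, from 2 at n = 2 to 28 at n = 99-100. The section sets no minimum follow-up for a subject to count in n and does not mention subjects whose outcome is pending. Its counting period is open-ended: "For the duration of therapy, any event that occurs and is at least possibly related to study treatment" counts if it meets the DLT criteria.

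Section 8.5.6 defines those criteria. Two of them take time to establish: "Grade 4 neutropenia and thrombocytopenia, not present prior to dosing, that last 28 days or longer should be considered a DLT", and "Delay of >2 weeks after Cycle 1 is complete due to drug-related toxicity". A drug-related non-hematologic event of Grade 3 or higher, apart from the listed gastrointestinal exceptions, can be declared at any time. For the DLT cohort, Section 4.1.1 says: "The DLT period will last the first 2 cycles of oral decitabine/cedazuridine treatment". It expects neutropenia and thrombocytopenia to be prominent among the DLTs, together with gastrointestinal toxicity and infection.

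**The concern.** A boundary of this kind has its tabulated properties when each subject's outcome is known as the subject is counted. Here n grows on the day a subject starts, while the DLT count grows weeks later. A subject who started last week adds to n almost as if already known to be free of DLT.

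Take 9 DLTs among the first 25 subjects. Table 17 has b = 9 for n = 22-25, so those 25 subjects meet the halting criterion. If nine more have started by the time the ninth DLT is declared, and none of the nine has a declared DLT yet, n = 34 and b = 12. Accrual continues, although nothing favourable has been learned about the nine.

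This is the only numerical toxicity stop once the DLT cohort closes. At stake is how many further subjects are enrolled on a regimen whose earlier subjects have already crossed the protocol's own line.

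**Working it through.** **1. Reproduce the stated figure.** Let S_n be the number of subjects with DLTs among the first n, each with a DLT independently with probability p and status known on entry. Carry P(S_n = s, not yet crossed) forward by P_n(s) = (1-p)P_{n-1}(s) + pP_{n-1}(s-1), and remove the mass with s >= b_n at each n from 1 to 100. With Table 17 and p = 0.20, the total mass removed is 0.1992. This matches the stated limit of 20%. On the same basis, crossing probability and mean number enrolled at the halt (100 if never halted) are 0.852 and 42.4 at p = 0.30, 0.999 and 16.9 at 0.40, and 1.000 and 9.2 at 0.50.

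**2. How many subjects are pending.** Accrual is not stated. Section 4.1 gives about 44 months in all, with the primary analysis about 8 months after enrolment of about 100 subjects. That leaves at most 36 months, or at least 100/36 = 2.8 subjects a month. I take 3, 5 and 8 a month. Over two 28-day cycles (56 days), the number pending is rate x 56/30.4, or about 5.5, 9 and 15 subjects. That lifts the boundary by about 1 to 4 DLTs.

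**3. The rule as written against an enrolment-order check.** The comparator halts if, for any k up to the number started, the first k subjects include b_k or more with declared DLTs. Both rules face the same reporting delay, so the difference comes from the rule alone. Assumptions are Poisson accrual, DLTs declared uniformly over days 7-56 or (late-declaring types) days 28-56, no dose change and no pause. Mean subjects started at the halt, at 5 a month, with simulation error of about one subject:

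| True DLT rate | Days 7-56: as written | Days 7-56: enrolment order | Days 28-56: as written | Days 28-56: enrolment order |
|---|---|---|---|---|
| 30% | 62 | 47 | 67 | 49 |
| 40% | 31 | 23 | 36 | 24 |
| 50% | 21 | 15 | 24 | 16 |

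Over 3-8 a month and both declaration patterns, the excess is about 10-25 subjects at 30%, 5-18 at 40% and 3-12 at 50%. The probability of ever halting at a 30% rate, at 5 a month with days 7-56, is 77% as written and 85% in enrolment order.

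**4. False halts at a 20% rate.** A crossing as written, with all n started and DLTs >= b_n, is also a crossing of the prefix k = n. The written rule therefore cannot cross more often than the enrolment-order rule. Once all outcomes are declared, the enrolment-order crossing event is the same as in step 1, so its probability is 0.1992 whatever the accrual. As written, the simulated probability is about 5-11%. Counting only halts before enrolment is complete, it falls to 2% at 8 a month with late declaration.

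**The case against.** - **No stated property fails.** Section 9.5 promises only a limit at a rate of about 20%, and the rule as written keeps it. It states no power or halt size at higher rates. This stands: the point is lost sensitivity, and it would be wrong to infer that the 20% limit is breached.
- **Recent subjects are not free of risk of a declared DLT.** Grade 3 or higher non-hematologic events can be declared early. A reader might infer that no new subject can yet have a DLT, but Section 8.5.6 does not support that. Their risk is partly observed, and the days 7-56 case allows for it.
- **The text could be read in enrolment order.** Nothing forbids that reading, but nothing states it either, and the plain reading of n is everyone who has started.
- **The 3+3 step comes first.** Two or more DLTs in the first six trigger a dosing reduction under Section 4.1.1. That has probability 1 - (1-p)^6 - 6p(1-p)^5 = 58%, 77% and 89% at 30%, 40% and 50%. Many simulated trials would not continue on unchanged dosing, so the sizes are upper-end. A pause after subject 6 alone changes little (40% rate, 5 a month: 30 to 28 with early declaration, 36 to 33 with late).
- **An enrolment-order check can collide with Section 4.1.1.** If subjects 1 and 2 have the only DLTs among six, b_2 = 2 halts accrual, while Section 4.1.1 calls for reduced dosing and three more subjects. A prefix crosses with only two or three DLTs in six with probability about 4% at a 20% rate and 10% at 40%. This stands and must be resolved in the text.
- **Other safeguards exist.** These are the DSRC reviews and ad hoc meetings (Section 1.1), safety at the 40-subject interim (Section 9.4), and sponsor discretion (Section 9.5). None has a numerical toxicity threshold or changes n.

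**Conclusion.** The point holds as a loss of sensitivity in the stopping rule. Followed as written, Section 9.5 lets accrual continue after earlier subjects have met the Table 17 boundary, because later starters with incomplete follow-up have raised it. The excess enrolment in step 3 rests on an assumed accrual of 3-8 a month, the two assumed declaration patterns, and no dose change or pause. It is largest when accrual is fast and DLTs declare late.

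A reader might also infer that a highly toxic regimen would go unchecked. It would not: at a 40% or 50% rate the written rule still halts almost every simulated trial, only later.

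**What to change.** In Section 9.5, state that each time a DLT is declared, Table 17 is applied in enrolment order: accrual halts if, for any k up to the number started, the first k subjects to start Cycle 1 include b_k or more with DLTs. Pending subjects then cannot hide a crossing among earlier ones.

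Three matters need reconciling in the same edit:
- which rule governs during the DLT cohort when Sections 9.5 and 4.1.1 point different ways;
- whether DLTs at an abandoned dosing level still count;
- the counting period. Section 9.5 counts events throughout therapy, while Section 8.5.6 calls the DLT period two cycles and then describes it as ending at Cycle 1 Day 28. This matters more under an enrolment-order check, because a late event in an early subject can trigger a halt.

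Do not instead count DLTs as they occur against only those subjects who have completed the window. Treating numerator and denominator differently raises the false-halt probability at a 20% rate to about 0.27-0.70 (early declaration, 2-10 subjects a month).

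The cost is a few sentences and a short monitoring program. Table 17 and the sample size do not change. The chance of halting at a true 20% rate rises from about 5-11% to the roughly 20% the protocol already accepts.

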**Table 17: Criteria for Excess Toxicity for an Acceptable Dose-limiting Toxicity Rate of 20%**

Number of Subjects, n	1	2	3-4	5-7	8-10	11-14	15-17	18-21	22-25	26-28
Boundary, b	-	2	3	4	5	6	7	8	9	10
Number of Subjects, n	29-32	33-36	37-40	41-44	45-48	49-52	53-56	57-60	61-64	65-69
Boundary, b	11	12	13	14	15	16	17	18	19	20
Number of Subjects, n	70-73	74-77	78-81	82-85	86-90	91-94	95-98	99-100		
Boundary, b	21	22	23	24	25	26	27	28		

## **10.0 SUPPORTING DOCUMENTATION AND OPERATIONAL CONSIDERATIONS**

### **10.1 Appendix 1: Regulatory, Ethical, and Study Oversight Considerations**

#### **10.1.1 Regulatory and Ethical Considerations**

- This study will be conducted in accordance with the protocol and with the following:
  - Consensus ethical principles derived from international guidelines including the Declaration of Helsinki and Council for International Organizations of Medical Sciences International Ethical Guidelines.
  - Applicable International Council for Harmonisation (ICH) Good Clinical Practice (GCP) Guidelines.
  - Applicable laws and regulations.
- The protocol, protocol amendments, ICF, IB, and other relevant documents (eg, advertisements) must be submitted to an IRB/IEC by the investigator and reviewed and approved by the IRB/IEC before the study is initiated.
- Any amendments to the protocol will require IRB/IEC approval before implementation of changes made to the study design, except for changes necessary to eliminate an immediate hazard to study subjects.
- The investigator will be responsible for the following:
  - Providing written summaries of the status of the study to the IRB/IEC annually or more frequently in accordance with the requirements, policies, and procedures established by the IRB/IEC.
  - Notifying the IRB/IEC of SAEs or other significant safety findings as required by IRB/IEC procedures.
  - Providing oversight of the conduct of the study at the site and adherence to requirements of 21 Code of Federal Regulations (CFR), ICH guidelines, the IRB/IEC, European regulation 536/2014 for clinical studies (if applicable), and all other applicable local regulations.

#### **10.1.2 Financial Disclosure**

Investigators and sub-investigators will provide the sponsor with sufficient, accurate financial information as requested to allow the sponsor to submit complete and accurate financial certification or disclosure statements to the appropriate regulatory authorities. Investigators are responsible for providing information on financial interests during the course of the study and for 1 year after completion of the study.

### **10.1.3 Informed Consent Process**

- The investigator or his/her representative will explain the nature of the study to the prospective subject or his/her legally authorized representative and answer all questions regarding the study.
- Subjects must be informed that their participation is voluntary. Subjects or their legally authorized representative [defined in 21 CFR 50.3 (L)] will be required to sign a statement of informed consent that meets the requirements of 21 CFR 50, local regulations, ICH guidelines, Health Insurance Portability and Accountability Act requirements, where applicable, and the IRB/IEC or study center.
- The medical record must include a statement that written informed consent was obtained before the subject was enrolled in the study and the date the written consent was obtained. The authorized person obtaining the informed consent must also sign the ICF.
- Subjects must be re-consented to the most current version of the ICF(s) during their participation in the study.
- A signed copy of the ICF(s) must be provided to the subject or the subject's legally authorized representative.

Subjects who are rescreened are required to sign a new ICF.

### **10.1.4 Data Protection**

- Subjects will be assigned a unique identifier by the sponsor. Any subject records or datasets that are transferred to the sponsor will contain the identifier only; subject names or any information which would make the subject identifiable will not be transferred.
- The subject must be informed that his/her personal study-related data will be used by the sponsor in accordance with local data protection law. The level of disclosure must also be explained to the subject.
- The subject must be informed that his/her medical records may be examined by Clinical Quality Assurance auditors or other authorized personnel appointed by the sponsor, by appropriate IRB/IEC members, and by inspectors from regulatory authorities.

### **10.1.5 Dissemination of Clinical Study Data**

All data generated in this study required to be publicly available will follow all local and global regulations. Requests to delay submission of study results will follow the appropriate regulatory procedures, if warranted.

Peer reviewed publication(s) of the study results will follow the publication policy detailed in Section 10.1.9.

#### **10.1.6 Data Quality Assurance**

- All subject data relating to the study will be recorded on printed or eCRF unless transmitted to the sponsor or designee electronically (eg, laboratory data). The investigator is responsible for verifying that data entries are accurate and correct by physically or electronically signing the eCRF.
- The investigator must maintain accurate documentation (source data) that supports the information entered in the eCRF.
- The investigator must permit study-related monitoring, audits, IRB/IEC review, and regulatory agency inspections and provide direct access to source data documents.
- Monitoring details describing strategy (eg, risk-based initiatives in operations and quality such as Risk Management and Mitigation Strategies and Analytical Risk-Based Monitoring), methods, responsibilities and requirements, including handling of noncompliance issues, study treatment storage and accountability, and monitoring techniques (central, remote, or on-site monitoring) are provided in the Monitoring Plan.
- The sponsor or designee is responsible for the data management of this study including quality checking of the data.
- The sponsor assumes accountability for actions delegated to other individuals (eg, Contract Research Organizations).
- Study monitors will perform ongoing source data verification to confirm that data entered into the eCRF by authorized site personnel are accurate, complete, and verifiable from source documents; that the safety and rights of subjects are being protected; and that the study is being conducted in accordance with the currently approved protocol and any other study agreements, ICH GCP, and all applicable regulatory requirements.
- Records and documents, including signed ICFs, pertaining to the conduct of this study must be retained by the investigator for 15 years after study completion unless local regulations or institutional policies require a longer retention period. No records may be destroyed during the retention period without the written approval of the sponsor. No records may be transferred to another location or party without written notification to the sponsor.

#### **10.1.7 Source Documents**

- Definition of source data: All information in original records and certified copies of original records of clinical findings, observations, or other activities in a clinical trial necessary for the reconstruction and evaluation of the trial.
- Source documents provide evidence for the existence of the participant and substantiate the integrity of the data collected. Source documents are filed at the study center.

- The goal is to maximize data transmitted directly from source to the EDC system. For data transcribed in the eCRF from source documents, the data must be consistent with the source documents or the discrepancies must be explained. The investigator may need to request previous medical records or transfer records, depending on the study. Also, current medical records must be available.

#### **10.1.8 Study and Site Closure**

The sponsor or designee reserves the right to close the study site or terminate the study at any time for any reason at the sole discretion of the sponsor. Study sites will be closed upon study completion. A study site is considered closed when all required documents and study supplies have been collected and a study-site closure visit has been performed.

The investigator may initiate study-site closure at any time, provided there is reasonable cause and sufficient notice is given in advance of the intended termination.

Reasons for the early closure of a study site by the sponsor or investigator may include but are not limited to:

- Failure of the investigator to comply with the protocol, the requirements of the IRB/IEC or local health authorities, the sponsor's procedures, or GCP guidelines.
- Inadequate recruitment of subjects by the investigator.
- Discontinuation of further study intervention development.

#### **10.1.9 Publication Policy**

- The results of this study may be published or presented at scientific meetings. If this is foreseen, the investigator agrees to submit all manuscripts or abstracts to the sponsor before submission. This allows the sponsor to protect proprietary information and to provide comments.
- The sponsor will comply with the requirements for publication of study results. In accordance with standard editorial and ethical practice, the sponsor will generally support publication of multicenter studies only in their entirety and not as individual site data. In this case, a coordinating investigator will be designated by mutual agreement.
- Authorship will be determined by mutual agreement and in line with International Committee of Medical Journal Editors authorship requirements.

